Visit #3: Patients will return to the clinic for AUTOPAP treatment set-up and education by trained study coordinator. Patients and their bed partner will receive a one-on-one standardized education session describing the method of applying the device and individualized mask fitting will be performed; (4) patients will be called twice weekly in the first two weeks and once weekly thereafter to troubleshoot barriers to AUTOPAP use and encourage daily treatment application including during daytime naps.

Visit #4: Patients will return to clinic for repeat PVT, FOSQ, ESS, CABP measurements and to initiate 24-hour ABP and urine collection. Patients will also be scheduled for repeat echocardiography test in the following 3 months, if they had a pre-treatment echocardiography (to assess AUTOPAP treatment effects). No caffeine will be permitted during visits 1 and 5 to minimize interference with EDS assessments. Patients will also do venous blood sampling (35 mL) for processing (DNA, RNA, serum, and plasma) and storage at UI Biorepository

Final Visit # 5: Patients will return to clinic in the morning after initiating 24-hour ABP and urine collection, which will be collected and processed/downloaded. AUTOPAP devices contain a software system that records the duration of AUTOPAP use each day. These data will be accessed and recorded as final measure of AUTOPAP treatment adherence.

Patients will be given instructions regarding follow-up care for OSA with sleep medicine or primary care provider.

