Treatment Related Measures 
 • Antihypertensive drugs: Adherence and Regimen Medication Possession Ratio (MPR) and Defined Daily Dose (DDD) • Adherence to AUTOPAP: Objective device download data at 90 days

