9.4 Statistical Analyses

9.4.1 Power and Sample Size Estimation: The primary goal of this initial study is to estimate differences in the effect size of AUTOPAP treatment on ABP and CABP in AA and EA's with moderate to severe OSA. Our preliminary data shows a reduction in office BP 3 months after AUTOPAP treatment and the effect size difference between-groups (by ethnicity; using differences in mean \pm SD change of BP and t-tests in PASS program, <http://www.ncss.com/pass.html>) was 0.42 for systolic and 0.53 for diastolic blood pressure. We determined that 99 patients in each group (total n = 198) will provide power of 0.8 in two-tailed tests with an alpha of 0.05 to observe a difference in effect size between groups of 0.4. Based on our prior experience we anticipate an attrition rate of 10-20%. Therefore, a total of 220 (198/0.90) patients enrolled will achieve the target of 198 patients completing the study. Our preliminary study of PM in our clinical population (selected with a positive BSQ) shows approximately 95% sensitivity and specificity of PM determined AHI of ≥ 15 /hour in terms of predicting PSG-determined AHI of ≥ 15 /hour (inclusion criteria). Therefore, we expect to screen approximately 260 patients (220/0.95).

9.4.2 Data analysis: A p-value < 0.05 will be considered significant. All variables and analysis goals are listed in table above. **Specific Aim 1.** Within group changes in primary and secondary outcomes will be assessed with repeated measures ANOVA implemented with PROC MIXED in SAS. A two-sample t-test (PROC TTEST in SAS) will be used to examine between-group differences in the treatment-related changes in primary and secondary outcomes. **Specific Aim 2.** Primary outcome will be assessed with a two-sample t-test (PROC TTEST in SAS). Secondary outcomes will be assessed with partial correlations implemented with PROC CORR in SAS.

Exploratory Aims 3. Effect of Individual Ancestry on changes in primary and secondary outcomes of specific aim 1 within group will be assessed with ANCOVA implemented with PROC GLM in SAS. Correlations (of VVI with AHI and change in VVI with change in AHI) will be assessed within groups.

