Residuals and outliers: Linear models require residuals from model fits to follow a normal distribution and be free of outliers. We will examine residual distributions and apply transformations to outcomes and explanatory variables as warranted to achieve normality. Further model checks will employ partial regression plots; outliers will be dealt through case removal, influence down-weighting (robust M-estimation), or bootstrapping of estimators. Missing data: We will examine patterns of missingness with respect to covariates and include any covariates differentially associated with missing data. Correctly specified linear mixed models yield unbiased estimates for data missing at random (MAR); multiple imputation can also be employed. It is possible that subjects' treatment experiences will affect missingness (dropout), in which case data is not missing at random (NMAR) or nonignorable, and requires additional modeling, such as pattern-mixture models.

Moderators: Whether a moderator variable Z affects the association of explanatory variable X and outcome Y will be examined by introducing Z and the $Z*X$ interaction in the linear model. When Z is a (0,1)-indicator variable (e.g., gender), the coefficient for Z is the adjustment to the intercept and the coefficient for $Z*X$ is the adjustment to the slope appropriate for the group coded 1; the latter coefficient tests the moderator effect.

Mediators: None hypothesized.

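### The primary AA-versus-Other comparison is a completers' t-test that the plan's missing-at-random method does not reach, so it can be biased if baseline-related dropout differs by race

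*Combined protocol and SAP*

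**What the plan says.** Section 9.4.2, Specific Aim 1, assigns two methods. Change within each group is analysed by repeated-measures ANOVA in PROC MIXED. For the comparison of the groups, "A two-sample t-test (PROC TTEST in SAS) will be used to examine between-group differences in the treatment-related changes in primary and secondary outcomes". The Section 8 table makes that comparison primary for 24-hour systolic and diastolic pressure.

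The missing-data paragraph of 9.4.2 then offers three things:

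- For MAR data: "Correctly specified linear mixed models yield unbiased estimates for data missing at random (MAR); multiple imputation can also be employed".
- After examining patterns of missingness, the analysts will "include any covariates differentially associated with missing data".
- If dropout is not at random, the analysis "requires additional modeling, such as pattern-mixture models".

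None of the three is linked to a named outcome or contrast. Section 9.4.1 expects 10-20% attrition, and the synopsis reports 2 of 16 so far (12.5%).

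**The concern.** The MAR argument belongs to a model that the race comparison does not use. A t-test on change drops every patient without a valid 3-month value, whether the patient left or the ambulatory recording failed. It also has no place for covariates. As written, then, neither the mixed-model argument nor the covariate step protects the trial's main result.

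This matters because change in blood pressure is correlated with baseline pressure: patients who start high tend to fall more. If dropout removes high-baseline patients from one race group more than from the other, the completers' mean change moves by different amounts, and the t-test reads the gap as a race difference. Race is not randomised, so the design does not ensure the same dropout mechanism in both groups.

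There is also a reporting problem. The within-group estimates would use all patients and the between-group estimate only completers, so the first two need not subtract to the third.

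**Working it through.** **1. The plan's own figures.** Section 9.4.1 states that "99 patients in each group (total n = 198) will provide power of 0.8 in two-tailed tests with an alpha of 0.05"; the assumed effect is a standardised difference of 0.4. By the normal formula, n = 2(1.960 + 0.842)² / 0.4² = 98.1, so 99 per group. The noncentral t gives 99.08, with power 0.7997 at 99. Enrolment: 198 / 0.90 = 220. Both figures reproduce, and both presume a t-test on completers. Enrolling 220, power is 0.80 at 10% attrition, 0.79 at 12.5% and 0.75 at 20%.

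**2. Assumptions not in the documents.** SD 15 mmHg at both visits, baseline/follow-up correlation r of 0.5 or 0.7, normal data. Dropout depends on race and observed baseline pressure only (so MAR holds), with log-odds rising by 1 per SD of baseline where it is baseline-related.

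- SD of change = 15 × √(2(1 − r)) = 15.0 (r = 0.5) or 11.6 (r = 0.7).
- Target difference = 0.4 × SD of change = 6.0 or 4.65 mmHg.

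**3. Bias of the completers' t-test.** If m is the completers' mean baseline in SD units from the group mean, the bias in (AA change − Other change) is (r − 1) × 15 × (m_AA − m_Other). Integrating the logistic dropout model over a normal baseline gives m = −0.173 at 20% dropout and −0.091 at 10%. Random dropout gives m = 0.

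| Dropout | Bias, r = 0.5 | Bias, r = 0.7 | Share of target |
|---|---|---|---|
| By race only, 20% AA vs 10% Other | 0 | 0 | 0 |
| Same mechanism, similar baselines, 12.5% each | 0 | 0 | 0 |
| Same slope, 20% AA vs 10% Other | 7.5 × 0.082 = 0.62 | 4.5 × 0.082 = 0.37 | 10% / 8% |
| Baseline-related in AA only, 20% vs 10% | 7.5 × 0.173 = 1.30 | 4.5 × 0.173 = 0.78 | 22% / 17% |

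Bias in mmHg is proportional to the SD; at SD 12 the last two rows become 0.49/0.30 and 1.04/0.62. The share of target does not depend on the SD. If the mechanism is identical but AA patients start 0.5 SD higher, the bias is 4-6% of target.

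**4. Error rates.** Simulation with 110 enrolled per group and no true difference (20,000 trials per case) gave these t-test rejection rates for r = 0.5 / 0.7:

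- race-only dropout: 5.0% / 5.0%
- same mechanism: 5.0% / 5.2%
- same slope, 20% vs 10%: 6.0% / 5.5%
- AA-only: 9.2% / 7.1%

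The maximum-likelihood race-by-visit estimate using all baselines stayed within 0.02 mmHg of zero throughout.

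**5. Direction and power.** In the AA-only case at r = 0.5, 8.5 of the 9.2 points are rejections showing a smaller fall in AA. Only 0.7 points favour the trial's hypothesis, against a nominal 2.5. With a true 0.4 SD effect and r = 0.6, t-test power is 0.80 (same mechanism, 12.5%), 0.70 (same slope, 20% vs 10%) and 0.59 (AA-only). Purely random dropout of 20% and 10% (88 and 99 completers) would give about 0.78, so most of the fall to 0.59 comes from bias rather than lost numbers.

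**The case against.** Several points on the other side are sound.

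- *A reader might infer that MAR dropout necessarily biases the race difference.* It does not. The bias vanishes when dropout depends on race alone, or on baseline in the same way in two groups with similar baselines. The documents report no dropout by race or by blood pressure.
- *A reader might infer that the plan has no valid MAR method for the contrast.* The quoted sentence also names multiple imputation, which could feed a two-sample comparison. What stands is that it is optional, has no imputation model, and is not attached to the race test.
- *A reader might infer that pattern-mixture models cannot work here because dropouts have no post-treatment value.* Such models always need an identifying assumption, and delta-adjusted imputation is one of them. The fair point is that the plan states no assumption.
- *A reader might infer that adherence is unknowable for dropouts.* The Section 8 table lists "Adherence to AUTOPAP: Objective device download data at 90 days", and Section 3 says of the device downloads at the final visit that "These data will be accessed and recorded as final measure of AUTOPAP treatment adherence". But the device logs use daily, nothing says that partial data are lost, and the plan does not say adherence would be the covariate chosen. This supports a precaution only.
- *Larger error rates can be produced.* Opposite baseline dependence in the two groups at 20% dropout each gives up to 2.6 mmHg and 21% rejection, but nothing in the documents suggests that pattern.

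Finally, the mixed model performs well above because the simulated dropout satisfies its assumptions. The mechanism the plan itself raises, dropout driven by experience of treatment, may be NMAR, and the mixed model does not cure that.

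None of this changes the assignment of methods: the primary contrast has no pre-specified analysis that is valid under MAR when baseline-related dropout differs by race.

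**Conclusion.** The point holds in a limited form. The completers' t-test can be biased under MAR; whether it will be, and in which direction, cannot be told from the documents. Under the stated assumptions the plausible size runs from zero, through about 0.4-0.6 mmHg (same slope, unequal dropout), to 0.8-1.3 mmHg with 7-9% rejection (baseline-related dropout in AA only).

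The documents do not support reading this as a route to false confirmation of the hypothesis. If higher-pressure AA patients drop out more, the error mainly attenuates the hypothesised larger AA fall and costs power. The sign reverses if lower-pressure AA patients drop out more. The change is worth making because a better analysis uses a procedure that the plan already names.

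**What to change.** In 9.4.2, Specific Aim 1:

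1. Make the race-by-visit contrast from PROC MIXED the primary between-group analysis. Include every patient with a valid baseline or follow-up value, use an unstructured within-patient covariance, and do not constrain the baseline means to be equal, since the groups are not randomised.
2. Keep the t-test as a completers' sensitivity analysis.
3. Limit covariates added because of missingness to those known at baseline. PROC MIXED drops records with a missing covariate, so a covariate read at the end of the study could remove the dropouts' baseline records.
4. Specify the NMAR pattern-mixture analysis for the same contrast, as delta-adjusted multiple imputation with the shift varied separately in AA and Other.

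The cost is revised analysis wording and a little more programming. No new data are needed and enrolment stays at 220. With complete data the estimated mean difference equals that of the t-test. With completely random dropout the gain is small: a standard error 1-2% lower. Item 1 does not protect against NMAR dropout, which is why item 4 is needed.

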10. ETHICAL CONSIDERATIONS

10.1 Declaration of Helsinki

The study will be conducted in accordance with the Declaration of Helsinki (1964) including all amendments up to and including the Scotland revision (2000) and notes of clarification added in 2002 and 2004 as described in Appendix D.

10.2 Good Clinical Practice and Regulatory Compliance

This study will be conducted in accordance with the principles of GCP (per the current ICH guidelines) and the requirements per JBVAMC R&D policies regarding the conduct of clinical trials and the protection of human patients.

10.3 IRB/Ethics Committee Approval

The PI will submit the protocol, the ICF, HIPAA and any other material used to inform patients about the trial to the IRB for approval prior to enrolling any patient into the trial. Approval must be in the form of a letter signed by the Chairperson of the IRB or the Chairperson's designee, must be on IRB stationary and must include the protocol by name and/or designated number. The protocol and ICF must be approved by the IRB committee before patients are screened for enrollment.

The PI will not amend the protocol without approval from the JBVAMC R&D office and IRB. Changes to the protocol must be in the form of a written amendment. These changes must be submitted by the PI to the IRB and such amendments will only be implemented after written approval of the requisite IRB. All amendments will also be submitted to VA regulatory authorities as required by JBVAMC R&D office.

The PI will submit all periodic reports and updates that the IRB/ JBVAMC R&D office may require, including any final reports.

10.4 Informed Consent

No study related procedures will be performed until a patient has given written informed consent. The ICF will clearly describe the potential risks and benefits of the study, in a language that the patient understands, and each prospective participant must be given adequate time to discuss the study with the PI or study coordinator and to decide whether or not to participate. Each patient who agrees to participate in the trial and who signs the ICF will be given a copy of the signed and dated document. The original copy of the signed and dated ICF will be retained by the PI in the study files.

The PI will also obtain authorization from the patient to use and/or disclose PHI in compliance with the HIPAA. Written HIPAA authorization will be obtained separately from the ICF.

If a protocol amendment substantially alters the study design or potential risk to the patient, the ICF will be revised and submitted to the IRB for review and approval; the revised form will be used to obtain consent from patients currently enrolled in the study if they are affected by the amendment; and the new form must be used to obtain consent from new patients prior to enrollment.

10.5 Departure from Protocol

When an emergency occurs that requires a departure from the protocol for an individual, a departure will be only for that patient. The PI in such an emergency will, if circumstances and time permit, contact the IRB/JBVA R&D office immediately by telephone. Such contacts will be made as soon as possible to permit a decision as to whether or not the patient (for whom the

departure from protocol was affected) is to continue in the study. The CRF and source documents will completely describe the departure from the protocol and state the reasons for such departure.

11. ADMINISTRATIVE

11.1 Study Monitoring

The study monitoring will be through regularly scheduled Data Safety Monitoring Committee (PI and Study coordinator/other key personnel, TBD) meetings and as per the JBVAMC R&D office regulations. They may include review of various aspects of the trial including, but not limited to, screening logs, compliance with the protocol and with the principles of GCP, completion of CRFs, source data verification, study data security and storage, facilities and staff.

11.2 Source Documents

The PI will maintain records separate from the CRFs in the form of clinical charts, laboratory reports, etc. (i.e., source documents). The PI will document in the clinical chart the name and number of the trial and the date on which the patient signed the ICF prior to the patient's participation in the study. Source documents will reflect the nature and extent of the patient's medical care relevant to this research protocol and will be available for source document verification against entries in the CRFs.

11.3 Record Retention

The PI will be responsible for maintaining the study records and the location and security of the study record storage. All records will be retained by the PI indefinitely per VA regulations after the completion of the study and in accordance with VHA's Records Control Schedule (RCS 10-1). PI will consult JBVAMC R&D office and VACO CSR&D (funding agency) prior to destruction of any research records. If paper records are destroyed, these paper documents will be placed in the secured document destruction box has been placed in room 6204, JBVAMC R&D.

Tissue samples collected for this research will be stored indefinitely at UI Biorepository.

11.4 Confidentiality

Patient medical information obtained as a result of this study is considered confidential and disclosure to third parties other than those noted below is prohibited.

Medical information resulting from a patient's participation in this study may be given to the patient's personal physician or to the appropriate medical personnel responsible for the patient's welfare.

Patient's medical information may be reviewed by government regulatory agency auditors, designated study auditor, or the IRB committee in the course of monitoring the conduct of the study. Every reasonable effort will be made to maintain such information as confidential.

The results of the study may be presented in reports, published in scientific journals or presented at medical meetings; however, patient names will never be used in any reports about the study.

APPENDIX I: SCHEDULE OF EVENTS

Table. Patient Schedule						
Procedures	Visits					
	1	2	3	4	5	6
Week	0-2			3-16		
Informed consent	x					
History and physical, anthropometrics	x					
Home portable monitoring (PM) test	x					
Determine AHI at termination of PM (≥ 15 /hour; enrolled)		x				
Central aortic blood pressure measurement (with brachial cuff), PVT x 2	x	x			x	
Venipuncture for blood sample (genotyping for AImS)		x			x	
Start 7-day actigraphy recording with sleep log		x			x	
Initiate 24-hour urine collection		x			x	
Initiate 24-hour ABP		x			x	
Collect and process: 24-hour urine, 24-hour ABP			x			x
Download 7-day actigraphy recording			x			x
Initiation of AUTOPAP with subject education				x		
Telephone contacts for AUTOPAP adherence optimization	Twice weekly x 4, then once/week					
Schedule Echocardiography		x			x	
Final visit and AUTOPAP adherence data download						x

APPENDIX II: QUESTIONNAIRES and TEST BATTERY

1. Epworth Sleepiness Scale (ESS)

This is a well-validated patientive rating scale for sleepiness, comprising 8 items each rated from 0 (no chance of dozing) to 3 (high chance of dozing). A total score of >10 is generally taken to indicate significant sleepiness. Patients for this protocol will be required to have an ESS score of ≥ 12 . The standard instruction asks a patient to refer to “your usual way of life in recent times”, when answering. This instruction will be modified, asking patients to refer to “the past two weeks”, which will be the interval between successive visits.

THE EPWORTH SLEEPINESS SCALE

How likely are you to doze off or fall asleep in the following situations, in contrast to feeling just tired? This refers to your usual way of life during the past two weeks. Even if you have not done some of these things recently, try to work out how they would have affected you. Use the following scale to choose the most appropriate number for each situation:

- 0 = no chance of dozing
- 1 = slight chance of dozing
- 2 = moderate chance of dozing
- 3 = high chance of dozing

SITUATION	CHANCE OF DOZING
Sitting and reading	_____
Watching TV	_____
Sitting inactive in a public place (e.g. a theater or a meeting)	_____
As a passenger in a car for an hour without a break	_____
Lying down to rest in the afternoon when circumstances permit	_____
Sitting and talking to someone	_____
Sitting quietly after lunch without alcohol	_____
In a car, while stopped for a few minutes in traffic	_____
Total	_____

2. Functional Outcomes of Sleep – Short Form (FOSQ-10)

The FOSQ-10 is a 10-item questionnaire, derived from the original 30-item FOSQ instrument, that has been specifically validated in patients with OSAS (Chasens et al. 2009). The FOSQ-10 is a quality of life instrument with subscales addressing the impact of sleepiness on: general productivity, activity level, vigilance, social outcomes, and intimacy and sexual relationships. Each subscale has a possible range of 1 – 4 and the total score has a possible range of 5 – 20. Higher scores indicate less impairment.

**FUNCTIONAL OUTCOMES OF SLEEP QUESTIONNAIRE
(FOSQ)**

Some people have difficulty performing everyday activities when they feel tired or sleepy. The purpose of this questionnaire is to find out if you generally have difficulty carrying out certain activities because you are too sleepy or tired. In this questionnaire, when the words “sleepy” or “tired” are used, it means the feeling that you can’t keep your eyes open, your head is droopy, that you want to “nod off”, or that you feel the urge to take a nap. These words do not refer to the tired or fatigued feeling you may have after you have exercised.

DIRECTIONS: Please put a () in the box for your answer to each question. Select only one answer for each question. Please try to be as accurate as possible. All information will be kept confidential.

(0) I don't do this activity for other reasons	(4) No difficulty	(3) Yes, a little difficulty	(2) Yes, moderate difficulty	(1) Yes, extreme difficulty
---	-------------------------	---------------------------------------	---------------------------------------	--------------------------------------

1. Do you have difficulty concentrating on the things you do because you are sleepy or tired?
2. Do you generally have difficulty remembering things, because you are sleepy or tired?
3. Do you have difficulty operating a motor vehicle for short distances (less than 100 miles) because you become sleepy or tired?
4. Do you have difficulty operating a motor vehicle for long distances (greater than 100 miles) because you become sleepy or tired?

				
				
				
				

Psychomotor Vigilance Task (PVT)

The PVT is a motor reaction time task and a test of sustained vigilance. The patient is given a hand-held device with a screen and is instructed to press the “space bar” every time a flash of numbers appears in the center of the screen. The intervals between these stimuli are randomized and when the space bar is pressed, the number displays the reaction time in milliseconds for a brief interval before the screen again goes blank. The task continues for 10 minutes.

Portable Monitoring (PM)

